### 7.1 Arm 1: mFOLFOX6 Plus Atezolizumab

The agents in the table below are listed in the order of intended administration.

Agent	Dose	Route	Duration	Days	Cycle
Atezolizumab	840mg*	IV	Over 60 min (+/- 15 min) for 1 st dose, then Over 30min (+/- 10 min) for all subsequent doses	Day 1	Every 14 days
Oxaliplatin	85mg/m 	IV	Over 2 hours (+/- 30 min)	Day 1	Every 14 days
Leucovorin**	400mg/m 	IV	Over 2 hours (+/- 30 min)	Day 1	Every 14 days
Fluorouracil	400mg/m  + 2400mg/m 	IV	Bolus + Over 46 hours (+/- 4 hours)	Day 1 + Days 1-3	Every 14 days

\* Patients 12 to < 18 years of age will receive a dose of 10 mg/kg up to a maximum flat dose of 840 mg. The patient's age on the day of treatment should be used to determine whether to use weight-based dosing.

\*\* Alternatively, leucovorin may be administered (via separate infusion containers) concurrently with oxaliplatin. Infusion duration may be adjusted according to institutional practice.

Note: If the minimum durations are followed and/or concurrent administration of leucovorin and oxaliplatin occurs, then fluorouracil administration could be completed on Days 1-2.

Atezolizumab should be the first drug administered regardless of cycle number as no premedication is allowed prior to the first dose of atezolizumab; see [Section 7.0](#) and [Section 8.1.4](#) for additional details.

Patients should receive 6 months (12 cycles total) of mFOLFOX6, including the cycle that may have been received prior to registration.

**For patients who started mFOLFOX6 after registration**, atezolizumab should start on Day 1 Cycle 1 of mFOLFOX6 (12 cycles in combination with mFOLFOX6 followed by 13 cycles as monotherapy for a total of 25 cycles of atezolizumab).

**For patients who receive one cycle of mFOLFOX6 prior to registration**, atezolizumab should start on Day 1 Cycle 2 of mFOLFOX6 (11 cycles in combination with mFOLFOX6 followed by 13 cycles as monotherapy for a total of 24 cycles of atezolizumab).

### 7.2 Arm 2: mFOLFOX6

The agents in the table below are listed in the order of intended administration.

Agent	Dose	Route	Duration	Days	Cycle
Oxaliplatin	85mg/m 	IV	Over 2 hours (+/- 30min)	Day 1	Every 14 days
Leucovorin*	400mg/m 	IV	Over 2 hours (+/- 30 min)	Day 1	Every 14 days
Fluorouracil	400mg/m  + 2400mg/m 	IV	Bolus + Over 46 hours (+/- 4 hours)	Day 1 + Days 1-3	Every 14 days

\* Alternatively, leucovorin may be administered (via separate infusion containers) concurrently with oxaliplatin. Infusion duration may be adjusted according to institutional practice.

Note: If the minimum durations are followed and/or concurrent administration of leucovorin and oxaliplatin occurs, then fluorouracil administration could be completed on Days 1-2.

Patients should receive 6 months (12 cycles total) of mFOLFOX6, including the cycle that may have been received prior to registration.

## 8.0 DOSE AND TREATMENT MODIFICATIONS

### 8.1 Ancillary Therapy, Concomitant Medications, and Supportive Care

**8.1.1 Patients should not receive any other agent which would be considered treatment for the primary neoplasm or impact the primary endpoint.**

**8.1.2 Patients should receive full supportive care while on this study.**

This includes blood product support, antibiotic treatment, and treatment of other newly diagnosed or concurrent medical conditions. All blood products and concomitant medications such as antidiarrheals, analgesics, and/or antiemetics received from the first day of study treatment administration until 30 days after the final dose will be recorded in the medical records.

**8.1.3 Treatment with hormones for cancer treatment or other chemotherapeutic agents may NOT be administered. Exceptions include:**

- Steroids given for adrenal failure (steroid supplementation should be at physiologic dosing or as described in [Section 8.1.12](#))
- Hormones administered for non-disease-related conditions (e.g. insulin for diabetes)
- Intermittent use of dexamethasone as an antiemetic (see [Section 8.1.4](#) for maximum dose requirements).

**8.1.4 Antiemetics may be used at the discretion of the attending physician, with the exception of steroids above.**

As this regimen has high emetogenic potential, it is recommended that all subjects on study should receive an aggressive prophylactic antiemetic regimen, consisting of a 5HT-3 antagonist +/- NK1 antagonist. Steroids are permitted for antiemetic prophylaxis during mFOLFOX6 chemotherapy, but must be limited to a maximum of equivalent dexamethasone 10 mg daily for 2 days every 14 days, see [Section 8.1.12](#) below for additional details.

**8.1.5 Diarrhea management is per the discretion of the treating physician.**

For symptoms of diarrhea (and/or abdominal cramping) that occur at any time during a treatment cycle, it is suggested that patients should be instructed to take an anti-diarrheal, such as loperamide. It is recommended that the anti-diarrheal should be started at the earliest sign of: (1) a poorly formed or loose stool; (2) an increase in bowel movements by 1 to 2 episodes per day compared to baseline, or (3) an increase in stool volume or liquidity. Additional anti-diarrheal measures may be implemented at the discretion of the treating physician. Patients should also be instructed to increase fluid intake to help maintain fluid and electrolyte balance during episodes of diarrhea, and IV

fluids should be considered for severe diarrhea, at the discretion of the treating physician.

**8.1.6 Radiation therapy may not be administered while a subject is on the study.**

**8.1.7 Surgery**

Patients who require surgery during protocol treatment may proceed as such, unless the surgery involves resection of recurrent colon cancer. Study drug can be held for a maximum of 42 days. If the patient requires an interruption of > 42 days, then they will be removed from protocol therapy.

**8.1.8 Alliance Policy Concerning the Use of Growth Factors**

- Please note that during treatment on mFOLFOX6, WBC growth factors are NOT required and may be used at the discretion of the physician.
- Blood products and growth factors should be utilized at the discretion of the treating physician as clinically warranted and following institutional policies and recommendations. The use of growth factors should follow published guidelines of the American Society of Clinical Oncology 2015 Clinical Practice Guidelines Update to the Recommendations for the Use of WBC Growth Factors. J Clin Oncol 33(28): 3199-212, 2015.
- The use of erythropoiesis-stimulating agents (ESAs) are NOT allowed, as this is an adjuvant therapy trial and use of ESAs is against the FDA label.
- If filgrastim/pegfilgrastim, tbo-filgrastim, or sargramostim are used, they must be obtained from commercial sources.

**8.1.9 Hypersensitivity/Infusion Reactions**

Chemotherapy infusion reactions: Treat hypersensitivity and infusion reactions as per institutional standards.

**8.1.10 Neurologic Toxicity Due to Oxaliplatin**

Patients receiving oxaliplatin on this study should be counseled to avoid cold drinks, chewing of ice chips, and exposure to cold water or air because the neurotoxicity often seen with oxaliplatin appears to be exacerbated by exposure to cold. The period of time during which the patient is at risk for these cold-induced sensory neuropathies is not well documented. Patients should exercise caution regarding cold exposure during the treatment period. Peripheral sensory neuropathies can occur at any time after receiving oxaliplatin therapy.

Supportive care is allowed at the discretion of the treating physician. For pharyngo-laryngeal dysesthesia, it is recommended to increase the duration of oxaliplatin infusion to 6 hours for subsequent cycles.

**8.1.11 Extravasation**

Extravasation of oxaliplatin has been associated with necrosis. Extravasation should be treated according to institutional guidelines.

**8.1.12 Fatigue**

Fatigue is the most common adverse event associated with immune checkpoint inhibitor therapy. This may be associated with a flu-like illness. Consider evaluation for associated or underlying organ involvement including pituitary disease, thyroid disease, and liver disease, or muscle inflammation.

**8.1.13 Fever**

Patients may experience isolated fever during infusion reactions or up to several days after infusion. Continued fever over the course of 1-2 weeks may represent autoimmune events, or infection. Appropriate workup should be initiated, at the discretion of the treating physician.

**8.1.14 Supplementation**

Electrolyte abnormalities should be adequately corrected with appropriate supplementation upon discovery.

**8.1.15 Vaccination**

Flu vaccine, pneumococcal vaccine, and any other relevant vaccines are recommended PRIOR to initiation of protocol therapy, at the discretion of the treating physician. Patients should not receive live attenuated vaccines while on study treatment.

**8.2 Dose Modification General Guidelines**

- If multiple adverse events are seen, administer dose based on greatest reduction required for a single adverse event observed. Reductions or holds for new cycles of treatment are based on treatment given in the preceding cycle and adverse events observed since the prior dose (with the exception of blood counts which should use Day 1 of cycle counts).
- Dose modifications of 5-FU, oxaliplatin, and atezolizumab may occur independently of each other, based on the pattern of toxicity. Patients unable to tolerate one or more drugs due to toxicity will remain on treatment with the other drugs. If oxaliplatin is omitted, 5-FU and leucovorin should both continue to be given.
- During mFOLFOX6, if 5-FU is omitted, leucovorin should also be omitted.
- Once the dose of any drug has been reduced, the dose cannot be re-escalated.
- There are no further dose reductions beyond those listed in the tables below for each drug. If further dose reduction is required, that drug should be discontinued.
- CTEP-AERS reporting may be required for some adverse events (see [Section 9.4](#)).
- **NOTE:** PRO-CTCAE data should not be used for determining attribution, dose modifications, or reporting of serious adverse events.

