**8.2.1 Dose Modifications for mFOLFOX6**

Dose Level	5-FU bolus (mg/m^2)	5-FU infusion (mg/m^2)	Leucovorin (mg/m^2)	Oxaliplatin (mg/m^2)
0*	400	2400	400	85
-1	320	1920	400	65
-2	270	1600	400	50
-3	230	1360	400	40

\*Dose level 0 refers to the starting dose. If 5-FU is skipped, leucovorin is also skipped.

If a dose reduction beyond level -3 is required for oxaliplatin, oxaliplatin will be discontinued. Continue 5-FU/leucovorin.

If a dose reduction beyond level -3 is required for 5-FU, discontinue mFOLFOX6.

If more than one dose reduction applies, use the most stringent (i.e. the greatest dose reduction).

If mFOLFOX6 is delayed due to toxicity for  $\geq 4$  weeks, counting from the originally scheduled day of treatment that was held, discontinue mFOLFOX6.

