**8.2.1.1 Hematologic Toxicity**

For **grade 2 neutrophil count decreased** on Day 1, delay 5FU and oxaliplatin until grade  $\leq 1$ , then resume oxaliplatin and 5FU at same dose.

For **grade 3 neutrophil count decreased** on Day 1, delay 5FU and oxaliplatin until grade  $\leq 1$ , then resume with one dose level decreased of oxaliplatin and 5FU.

For **recurring grade 3 neutrophil count decreased**, delay 5FU and oxaliplatin until grade  $\leq 1$ , then discontinue 5FU bolus and resume 5FU infusion and oxaliplatin with one dose level decreased.

For **grade 4 neutrophil count decreased or febrile neutropenia (defined as grade 3 or 4 neutropenia and  $T \geq 38.5^{\circ}\text{C}$ )**, delay 5FU and oxaliplatin until grade  $\leq 1$ , then discontinue 5FU bolus and resume 5FU infusion and oxaliplatin with one dose level decreased.

For **recurring grade 4 neutrophil count decreased or recurring febrile neutropenia**, delay 5FU and oxaliplatin until grade  $\leq 1$ , then discontinue 5FU bolus and resume 5FU infusion and oxaliplatin with two dose levels decreased.

For **grade 2 platelet count decreased**, delay 5FU and oxaliplatin until grade  $\leq 1$ , then resume oxaliplatin with one dose level decreased and 5FU at same dose.

For **grade 3 or 4 platelet count decreased**, delay 5FU and oxaliplatin until grade  $\leq 1$ , then resume 5FU and oxaliplatin with one dose level decreased.

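### Section 8.2 contradicts 8.2.1 on whether oxaliplatin stops when 5-FU must go below level -3, and its Day 1 blood-count rule does not match the count lines of 8.2.1.1

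*Combined protocol and SAP*

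**What the plan says.** Section 8.2 sets the general rules. Changes for a new cycle depend on the treatment given in the preceding cycle and on "adverse events observed since the prior dose (with the exception of blood counts which should use Day 1 of cycle counts". For a drug that has used up its listed levels it says: "If further dose reduction is required, that drug should be discontinued". It also says: "Patients unable to tolerate one or more drugs due to toxicity will remain on treatment with the other drugs". Only one companion is named for a 5-FU omission: "During mFOLFOX6, if 5-FU is omitted, leucovorin should also be omitted".

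Section 8.2.1 lists the mFOLFOX6 dose levels and then gives its own rule for the same floor: "If a dose reduction beyond level -3 is required for 5-FU, discontinue mFOLFOX6".

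Section 8.2.1.1 gives the count-based lines. The Grade 2 and first Grade 3 neutrophil lines read "on Day 1, delay 5FU and oxaliplatin until grade" 1 or lower. The next severity up carries no timing. That line covers "grade 4 neutrophil count decreased or febrile neutropenia (defined as grade 3 or 4 neutropenia and" a temperature of at least 38.5 °C. It asks for a delay until recovery, "then discontinue 5FU bolus and resume 5FU infusion and oxaliplatin with one dose level decreased".

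**The concern.** Both pairs of rules apply to the chemotherapy backbone, which is common to the two arms. If two sites can read the same protocol and give different chemotherapy after the same event, delivered dose varies by site for reasons unrelated to the patient.

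There is also a compliance consequence. Section 6.1 asks sites to report major and critical deviations, but where the text gives two answers nobody can say which action deviates.

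The first pair decides whether oxaliplatin ends when 5-FU does. The second decides whether a low count seen between cycles, and gone by the next dosing day, changes the dose at all. Because 8.2 does not allow a reduced dose to be raised again, a site that takes the reducing reading commits the patient to at most that level for every later cycle.

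**Working it through.** No alpha, power or event count is involved. The check sets the rules side by side and uses the dose table in 8.2.1.

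**Part 1: 5-FU at level -3 and a further reduction is needed**

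| Source | 5-FU | Leucovorin | Oxaliplatin |
|---|---|---|---|
| 8.2 | stop | stop (follows 5-FU) | continue, as one of the other drugs |
| 8.2.1 | stop | stop | stop, as part of mFOLFOX6 |

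The case can arise while oxaliplatin is still being given. The Grade 3 diarrhea line (8.2.1.2) and the Grade 3 mucositis line (8.2.1.3) lower 5-FU alone, so 5-FU can reach its floor with oxaliplatin at any listed level: 85, 65, 50 or 40 mg/m². The two rules then differ by the whole oxaliplatin dose, 40 to 85 mg/m² against 0, in each remaining mFOLFOX6 cycle.

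I looked for a tie-breaker:

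- 8.2.1 tells sites to take the larger reduction when several apply. That ranks reductions; it does not say whether a second drug stops.
- Appendix III sends sites to Section 8.0 as a whole from Cycle 2.
- The German appendix (2.3.3, 2.4.3, 2.5.3) points to Section 8.2 as a whole. Its preface says that its sections with precedence over the protocol are marked, but nothing ranks 8.2 against 8.2.1.

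**Part 2: which count lines carry a Day 1 condition**

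| Line in 8.2.1.1 | Day 1 written? | Dose on resuming |
|---|---|---|
| Neutrophils, Grade 2 | yes | both drugs unchanged |
| Neutrophils, first Grade 3 | yes | both one level lower |
| Neutrophils, recurring Grade 3 | no | bolus stopped; infusion and oxaliplatin one level lower |
| Neutrophils, Grade 4 | no | bolus stopped; infusion and oxaliplatin one level lower |
| Neutrophils, recurring Grade 4 | no | bolus stopped; infusion and oxaliplatin two levels lower |
| Platelets, Grade 2 | no | oxaliplatin one level lower, 5-FU unchanged |
| Platelets, Grade 3 or 4 | no | both one level lower |

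Take a first Grade 4 neutrophil count between cycles, without fever, recovered by Day 1, at level 0:

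- With the 8.2 Day 1 rule applied: no change. 5-FU is 400 + 2400 = 2800 mg/m²; oxaliplatin is 85 mg/m².
- With 8.2.1.1 as worded: 5-FU is 0 + 1920 = 1920 mg/m²; oxaliplatin is 65 mg/m².
- Difference in 5-FU: (2800 - 1920)/2800 = 880/2800 = 31%.
- Difference in oxaliplatin: (85 - 65)/85 = 20/85 = 24%.

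With 12 cycles planned, an event after Cycle 1 leaves 12 - 1 = 11 cycles affected. That is the ceiling; later events affect fewer.

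**The case against.** **On 5-FU below level -3.** The 8.2.1 line is written for exactly this event. Beside it stands a deliberately different line for oxaliplatin, under which 5-FU and leucovorin go on. Section 8.2 shows the same asymmetry: it states that 5-FU and leucovorin continue without oxaliplatin, and has no mirror sentence for oxaliplatin without 5-FU. Its allowance for independent modification is permissive and also serves atezolizumab. A site at this point would probably be reading 8.2.1. All of this stands as evidence that the 8.2.1 wording was intended. It does not remove the two sentences in 8.2 that say otherwise, and the convention that a specific rule overrides a general one is not stated.

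**On the counts.** No line in 8.2.1.1 says that a count at any time in the cycle triggers it, so the general rule may fill the silence. Delaying treatment until recovery fits a count that is low when dosing is due. The Study Calendar (5.0) schedules blood counts on Day 1 and requires none between cycles, so the question arises only after an unscheduled test. This stands, and it is why Part 2 is a mismatch and not a contradiction. Against it, if 8.2 governs every line, the Day 1 wording in the first two neutrophil lines does no work; its selective use invites the other reading.

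**Stronger readings that a reader might infer.** Febrile neutropenia shares a line with the Grade 4 count, so it may seem to conflict with 8.2 as well. The documents do not support that. The 8.2 exception covers blood counts only. Febrile neutropenia is defined in 8.2.1.1 by neutropenia plus fever, and the adverse event listing in 9.4 places it under blood and lymphatic disorders, apart from decreased neutrophil count under investigations. Section 8.2 therefore counts it as an event since the prior dose, which agrees with 8.2.1.1. Nor does a site's first reading fix the dose in both directions: only a reduction is irreversible, and an unchanged dose can still be lowered later. Finally, the rules are the same in both arms, and nothing in the documents shows an effect on the comparison of DFS or OS.

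**Conclusion.** The point holds in two parts of different strength.

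- **5-FU below level -3:** a direct contradiction between 8.2 and 8.2.1 about oxaliplatin, with no stated precedence. It applies only to patients who have exhausted all three listed 5-FU reductions and need another. The documents do not say how many that would be.
- **Grade 4 neutrophil counts between cycles, and the other count lines without a Day 1 condition:** an unresolved mismatch that can be read either way. For a first Grade 4 event at level 0, the readings differ by 31% in 5-FU and 24% in oxaliplatin per cycle, measured against the unchanged dose. This assumes a count taken outside the scheduled Day 1 test and recovered by Day 1. The frequency is again not given.

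Febrile neutropenia is not part of the finding. This is a matter of internal consistency in the treatment rules that should be corrected. It is not a flaw in the statistical design, and no view is taken on which dose rule is right.

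**What to change.** Reconcile the three sections; the sponsor decides which clinical rule stands.

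1. Make 8.2 and 8.2.1 say the same thing about oxaliplatin when 5-FU passes level -3. If the two are meant to differ, state in 8.2 which section prevails.
2. State whether the Day 1 count rule in 8.2 applies to each count-based line of 8.2.1.1: Grade 4 neutrophils, recurring Grade 3 and Grade 4 neutrophils, and both platelet lines. Word the timing in the same way in every line.
3. Because Grade 4 counts and febrile neutropenia share a line, both for a first and for a recurring event, make clear that any timing condition on counts concerns the count and not the febrile event, unless the sponsor intends otherwise.

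The cost is a few words in 8.2, 8.2.1 and 8.2.1.1. No visit, test or analysis changes.

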**8.2.1 Dose Modifications for mFOLFOX6**

Dose Level	5-FU bolus (mg/m^2)	5-FU infusion (mg/m^2)	Leucovorin (mg/m^2)	Oxaliplatin (mg/m^2)
0*	400	2400	400	85
-1	320	1920	400	65
-2	270	1600	400	50
-3	230	1360	400	40

\*Dose level 0 refers to the starting dose. If 5-FU is skipped, leucovorin is also skipped.

If a dose reduction beyond level -3 is required for oxaliplatin, oxaliplatin will be discontinued. Continue 5-FU/leucovorin.

If a dose reduction beyond level -3 is required for 5-FU, discontinue mFOLFOX6.

If more than one dose reduction applies, use the most stringent (i.e. the greatest dose reduction).

If mFOLFOX6 is delayed due to toxicity for  $\geq 4$  weeks, counting from the originally scheduled day of treatment that was held, discontinue mFOLFOX6.

**8.2.1.1 Hematologic Toxicity**

For **grade 2 neutrophil count decreased** on Day 1, delay 5FU and oxaliplatin until grade  $\leq 1$ , then resume oxaliplatin and 5FU at same dose.

For **grade 3 neutrophil count decreased** on Day 1, delay 5FU and oxaliplatin until grade  $\leq 1$ , then resume with one dose level decreased of oxaliplatin and 5FU.

For **recurring grade 3 neutrophil count decreased**, delay 5FU and oxaliplatin until grade  $\leq 1$ , then discontinue 5FU bolus and resume 5FU infusion and oxaliplatin with one dose level decreased.

For **grade 4 neutrophil count decreased or febrile neutropenia (defined as grade 3 or 4 neutropenia and  $T \geq 38.5^{\circ}\text{C}$ )**, delay 5FU and oxaliplatin until grade  $\leq 1$ , then discontinue 5FU bolus and resume 5FU infusion and oxaliplatin with one dose level decreased.

For **recurring grade 4 neutrophil count decreased or recurring febrile neutropenia**, delay 5FU and oxaliplatin until grade  $\leq 1$ , then discontinue 5FU bolus and resume 5FU infusion and oxaliplatin with two dose levels decreased.

For **grade 2 platelet count decreased**, delay 5FU and oxaliplatin until grade  $\leq 1$ , then resume oxaliplatin with one dose level decreased and 5FU at same dose.

For **grade 3 or 4 platelet count decreased**, delay 5FU and oxaliplatin until grade  $\leq 1$ , then resume 5FU and oxaliplatin with one dose level decreased.

**8.2.1.2 Gastrointestinal Toxicity with Optimal Medical Management**

For **grade 2 diarrhea**, delay 5FU and oxaliplatin until recovery to grade  $\leq 1$ , then resume 5FU and oxaliplatin at the same dose level.

For **grade 3 diarrhea**, delay 5FU and oxaliplatin until recovery to grade  $\leq 1$ , then resume oxaliplatin at the same dose level and 5FU with one dose level decreased.

For **grade 4 diarrhea**, delay 5FU and oxaliplatin until recovery to grade  $\leq 1$  or baseline, then resume 5FU and oxaliplatin at the next lower dose level.

For **grade 3 nausea or vomiting or grade 4 vomiting**, delay 5FU and oxaliplatin until recovery to grade  $\leq 1$ , then resume 5FU and oxaliplatin at the next lower dose level.

